3.4 Treatment Measurements

For the first 1100 recruits (recruited before January 2015), arm volume will be measured at baseline, 1, 3, 6, 9 and 12 months then 6 monthly thereafter to 2 years, followed by annual measurements to 5 years using perometer arm scanning (and circumferential tape measurement of arm girth with anatomic landmarks (e.g. lateral epicondyle) as reference points). The contralateral arm will act as a control. *For the additional 300 patients (recruited from February 2015, on version 3.1 or higher of the patient information leaflet), these measurements will take place at baseline, 1, 3, 6, and 9 months only.*

Patients developing a 4-8.9% increase in arm volume within 9 months of arm surgery will be offered randomisation. Within the same visit, patients will undergo multi-frequency bioimpedance measurements, comparing the affected arm with the contralateral arm and the leg. Bioimpedance measurements will not lead to change of treatment but will be recorded and performed according to the trial Standard Operating Procedures (please note, Bioimpedance will only be measured in

the 1100 patients who are part of the 5 year study. Subsequent patients, who will only be followed up for 9 months, will not undergo this assessment).

Perometer measurements demonstrating an increase in arm volume >10% (on two occasions) will be utilised to commence treatment for lymphoedema.

For the first 1100 participants, FACT B+4 questionnaires will be administered at all visits apart from the 1 month visit to permit calculation of Trial Outcome Index (FACT B TOD following the ATAC Trial methodology. ^[PG 60] A lymphoedema symptom questionnaire will be administered at the same time points. EQ5D questionnaires will be administered at all time points apart from months 3, 36, 48 and 60.

Please note, quality of life questionnaires will only be administered at baseline for the final 300 participants.

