5 STATISTICAL ANALYSIS

Analysis 1 and 2 will directly compare BEA and perometer assessment at a given time point (6 and 18 months). The reported concordance/correlation in small series is 0.93¹³⁴¹. Thus, even if a sleeve has been applied in patients before 6 months' measurements and the arm circumference has been reduced, the reduction in fluid in the arm should have reduced both the perometer and BEA scores concomitantly.

Sample Size Calculation

We estimate 1100 women are needed for screening by perometer to recruit 270 women to the PLACE trial and this sample size of 1100 (derived from having approached 1500 women to take part in the study) allows us to assess equivalence for sensitivity and specificity for BEA compared to perometer measurement with tight confidence intervals. Previous reported correlation between the techniques is very high¹¹⁵, and this sample size allows us to have a 95% Confidence Interval (CI) around our sensitivity and specificity estimates such that they are $\pm 5\%$ or less. Thus if perometer and BEA are equivalent in sensitivity and specificity to within 5% of each other, we would expect that the BEA would become the preferred option as it would be mobile, non-invasive and simpler to use in any outpatient setting compared to a fixed, large instrument, such as the perometer. There will be less patients with lymphoedema at 6 months but nonetheless if BEA sensitivity is 95% of the perometer sensitivity, we can demonstrate this with a 95% CI of 91.42% to 97.49%. If the BEA sensitivity rate was as low as 90%, we would have a 95% CI of 85.12% to 93.49%. All subsequent analyses will use sample sizes based on larger numbers as there will be more lymphoedema events at 18 months and again at 36 months but their confidence intervals are within $\pm 5\%$. We have used the exact method for calculating confidence intervals for a binomial proportion (Documenta Geigy Scientific tables page 185 equation 769); the actual calculation was done using the www.measuringusability.com/wald.htm website calculator.

The sample will allow us to measure accurately, inter- and intra-technique variability at different time points.

Analyses 1 to 3 will assess whether BEA can be used instead of perometer in defining lymphoedema status. The second group of analyses is to look for any variables collected at operation or in the first 6 months post operation that singly or in combination can be used to predict lymphoedema status at or beyond 18 months.

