All percentages for the 3 groups (A-C) are estimated from ALMANAC Trial data (see Annex 4d). None of the analyses outlined will use cases where a treatment for lymphoedema has been given prior to 6 months as explained above. A "treatment paradox" will not affect analyses 1 to 3 and treatment will be a variable in analysis. Potentially, the predictive value of a measurement at 6 months by perometry of the arm may be altered by treatment when assessing lymphoedema at 18 or 36 months. We do not believe this will occur for the majority of patients but in any case we will take account of this in the Cox multivariate regression analysis based on perometer measurements at 18 and 36 months and by looking at variables which include treatment with a compression sleeve. As we indicated in the flow diagram of this study, 3 possibilities may arise:

- Group A: Women in whom the arm volume increase is less than 4% at all time points up to 6 months (approximately 33% of the population; 330 individuals). None of these patients will undergo treatment within the first 6 months and therefore the measurement at 6 months will not be subject to "treatment paradox" and should they subsequently develop lymphoedema before 18 months, they will be registered as having developed the lymphoedema event in a time-dependant manner for the multivariate analysis and subsequent treatment will not affect this analysis.
- Group B: Women who will have developed a 4-10% arm volume increase by 6 months (estimated as 46% of the total group; 460 patients). Around 135 women from this group (with a 4-8.9% volume increase) will go into the PLACE trial and have a sleeve applied and a similar number will go into the PLACE trial and will not have an arm sleeve applied.

Thus, in this group there will be 325 patients (460 minus 135) who are not treated until they develop lymphoedema and will not have a "treatment paradox" for the same reason as previously described. Out of the 135 cases allocated to the sleeve arm within the PLACE trial, who are chosen at random, we will use their data in a multivariate analysis as we will incorporate it as a factor, sleeve versus no sleeve in building the model.

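### PLACE is offered up to 9 months but Section 5 groups women at 6 months, so Group A can include women sleeved before any lymphoedema event, and its counts allow for none

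*Protocol*

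**What the plan says.** **Offer window.** Protocol Section 3.4: "Patients developing a 4-8.9% increase in arm volume within 9 months of arm surgery will be offered randomisation". The same section schedules a perometer reading at 9 months.

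**Grouping.** Section 5 sorts women by their readings up to 6 months. Group A stays below 4% throughout (33%, 330 women), Group B reaches 4-10% (46%, 460 women), and Group C exceeds 10% (about 210 women).

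**Treatment in Group A.** Section 5 says of these women: "None of these patients will undergo treatment within the first 6 months". A woman who later develops lymphoedema before 18 months is to be entered as a time-dependent event "for the multivariate analysis and subsequent treatment will not affect this analysis".

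**Where PLACE entrants come from.** In the Group B paragraph: "Around 135 women from this group (with a 4-8.9% volume increase) will go into the PLACE trial and have a sleeve applied", with a similar number randomised to no sleeve. It then says that "in this group there will be 325 patients (460 minus 135) who are not treated until they develop lymphoedema". The sample size text gives the PLACE target: "We estimate 1100 women are needed for screening by perometer to recruit 270 women to the PLACE trial".

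**Sleeve handling.** Analysis 4 (Cox regression) includes a sleeve versus no-sleeve factor for cases treated in PLACE, and excludes women who develop lymphoedema before 6 months. Section 2.0 plans a further comparison in the <4% group, of 6-month bioimpedance (BEA) and perometer readings as predictors of the 18-month outcome. No sleeve handling is stated there.

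**The concern.** Section 5 reasons that treatment cannot distort a time-to-first-event analysis in Group A because the event is already recorded when treatment starts. A PLACE sleeve is different: it is applied at 4-8.9%, before any event. A woman below 4% through 6 months who reaches that range at 9 months belongs to Group A by definition and is offered PLACE under Section 3.4.

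Such a sleeve falls between the 6-month predictor and the 18-month outcome, in women whose swelling has just begun. Section 1.4 cites an observational study in which compression garments were followed by a 4.1% arm reduction. On the protocol's own evidence, then, a sleeve could keep some women under the 10% threshold. If so, a woman missed by the perometer at 6 months would be scored as correctly negative, and one correctly flagged by BEA at 6 months would be scored as a false positive. The comparison of the two methods in this group would then partly reflect treatment.

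**Working it through.** **1. Reproduce the plan's counts.** On a base of 1000:
- Groups: 0.33 × 1000 = 330; 0.46 × 1000 = 460; 0.21 × 1000 = 210; total 1000.
- PLACE: 270 / 2 = 135 per arm.
- Group B not sleeved: 460 − 135 = 325.

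All agree with Section 5. The 135 sleeved women and a similar number of controls make up the whole PLACE target of 270, and all are placed in Group B. Section 5 therefore counts no PLACE entrants in Group A.

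**2. Set the windows side by side.**

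| Item | Window | Source |
|---|---|---|
| PLACE offer | 4-8.9% within 9 months | Section 3.4 |
| Group A and B definition | readings up to 6 months | Section 5 |
| Group A stated to be untreated | first 6 months only | Section 5 |
| Exclusion of cases already treated | before 6 months | Section 5 |

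None of the Section 5 items reaches a sleeve started at about 9 months.

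**3. Illustrative size.** Sleeved women in Group A = N × f × u × 1/2, where:
- N = 330 (Section 5).
- f = share of Group A first reaching 4-8.9% at 9 months. The protocol does not give it; 5-30% is assumed.
- u = PLACE uptake. It is not given for Group A; 30-59% is assumed. The upper value is 270 / 460 = 0.587, the uptake implied by the Group B accounting.
- 1/2 = 1:1 allocation, as implied by 135 sleeved and a similar number not.

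| f | u | Calculation | Sleeved | % of Group A |
|---|---|---|---|---|
| 5% | 30% | 330 × 0.05 × 0.30 / 2 | 2.5 | 0.8 |
| 10% | 59% | 330 × 0.10 × 0.587 / 2 | 9.7 | 2.9 |
| 20% | 59% | 330 × 0.20 × 0.587 / 2 | 19.4 | 5.9 |
| 30% | 59% | 330 × 0.30 × 0.587 / 2 | 29.1 | 8.8 |

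**4. What the Cox factor does.** It is not restricted to Group B, so a Group A woman sleeved through PLACE would carry it. The protocol does not say that it is time-dependent. Entered as a fixed factor, it labels her sleeved from the start, although she had to stay event-free until about month 9 to receive the sleeve. With events before 6 months excluded, the misclassification acts on risk sets between 6 and about 9 months. It flatters the sleeve there and so distorts the adjustment.

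**The case against.** The strongest reply is that the Group A sentence is conditional. It speaks of women who go on to develop lymphoedema and are registered as events, so the later treatment it means is most naturally treatment after the event. In that sense it is correct for a time-to-first-event model. This stands: the sentence needs limiting, not deleting. A reader might infer that the protocol declares Group A free of every treatment effect, but the text does not go that far. What it does is leave out the 9-month PLACE entrant.

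Second, Section 5 concedes that treatment may alter the predictive value of a 6-month reading and says the Cox model will take account of it. This also stands, and it leaves only the timing of the sleeve open in Analysis 4. It does not reach the Section 2.0 comparison.

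Third, the scope is limited. The groups do not define the primary endpoint, and Analyses 1 to 3 compare readings taken at the same visit, so a 9-month sleeve in Group A does not bias them in this way.

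Fourth, a reader might take full uptake and arrive at about 50 sleeved women (330 × 0.30 / 2 = 49.5). The documents do not support that. The plan's own accounting implies about 59%, the appended qualitative study plan reports difficulty recruiting to PLACE, and Section 7 requires a confirmatory duplicate measurement before randomisation, which would reduce the share qualifying.

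**Conclusion.** The mismatch between Sections 3.4 and 5 is real. Group A can contain women given a PLACE sleeve before any lymphoedema event, and Section 5 counts none. The illustrative range is about 2 to 29 women, or 0.8% to 8.8% of Group A. It rests on assumed values for the share newly reaching 4-8.9% and for uptake. The documents do not show that Group A will contain such women.

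Analysis 4 is partly protected by its sleeve factor. The Section 2.0 comparison in the <4% group is the more exposed.

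A reader might also infer that the expected low event rate in Group A is a product of treatment. That does not follow: the protocol gives neither the risk in women first swelling at 9 months nor the sleeve's effect on the 18-month outcome, so women sleeved cannot be converted into events lost. This is a worthwhile, inexpensive correction to secondary analyses and does not threaten the primary endpoint.

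**What to change.** 1. Reconcile the 9-month offer in Section 3.4 with the 6-month grouping and PLACE accounting in Section 5. Which window applies is the sponsor's choice.
2. In the Group A paragraph, limit the statement that treatment has no effect to treatment started after a registered lymphoedema event.
3. In Analysis 4, enter the sleeve term as time-dependent from the PLACE allocation date for all PLACE cases, including any in Group A.
4. In the Section 2.0 comparison for the <4% group, show the PLACE-sleeved women separately, or exclude them in a sensitivity analysis.

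The cost is some rewording, use of PLACE allocation dates, a little extra analysis and slightly fewer unsleeved Group A events. No new patient data are needed.

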6 SAFETY REPORTING PROCEDURES

6.2 Adverse Events

An **Adverse Event (AE)** is defined as any untoward medical occurrence in a participant to whom a research procedure has been administered, including occurrences which are not necessarily caused by or related to that procedure.

In research involving medical devices, a **Serious Adverse Event (SAE)** is an untoward occurrence that:

- Results in death;
- Is life-threatening*;
- Requires in-patient hospitalisation or prolongation of existing hospitalisation**
- Results in persistent or significant disability or incapacity, or;
- Consists of a congenital anomaly or birth defect;
- Other important medical events***.

*life-threatening' in the definition of 'serious' refers to an event in which the patient was at risk of death at the time of the event; it does not refer to an event which hypothetically might have caused death if it were more severe.

**Hospitalisation is defined as an inpatient admission, regardless of length of stay, even if the hospitalisation is a precautionary measure for continued observation. Hospitalisations for a pre-existing condition, including elective procedures that have not worsened, do not constitute an SAE.

***Other important medical events that may not result in death, be life-threatening, or require hospitalisation may be considered a serious adverse event/experience when, based upon appropriate medical judgment, they may jeopardise the subject and may require medical or surgical intervention to prevent one of the outcomes listed in this definition.

Adverse events can be either:

- '**related**' or '**unrelated**' i.e. resulted from administration of the medical device, or;
- '**expected**' or '**unexpected**' i.e. a type of event that is not listed in the protocol as an expected occurrence.

6.3 Adverse Event Reporting

Only adverse events/reactions **specifically related to the device** should be reported.

Do not report any complications or side effects commonly associated with cancer and/or chemotherapy e.g. septicaemia, neutropenia, deep vein thrombosis and hospitalisation due to viral illness.

All device-related SAEs must be reported immediately by the local Investigator to the Chief Investigator. The site should:

- Either, complete the SAE case report form, signed and dated and send immediately (within 24 hours or the next working day, preferably by fax on [name]) to the sponsor together with relevant treatment forms and anonymised copies of all relevant investigations.
- Or, contact the sponsor by telephone and then send the completed SAE form to the sponsor within the following 24 hours as above.

The form asks for nature of event, date of onset, severity, corrective therapies given, outcome and causality (i.e. unrelated, unlikely, possible, probably, definitely and not assessable). The responsible investigator should sign the causality of the event. Additional information should be sent within 5 days if the reaction has not resolved at the time of reporting.

The sponsor will provide the Main REC with an annual report of all SAEs. Investigators should report any SAEs as required by their Main Research Ethics Committee and/or Research & Development Office.

NB. Only adverse events e.g. illness, injury and accident specifically related to the device should be reported.

Any questions concerning adverse event reporting should be directed to the Chief Investigator in the first instance.

To report an SAE, an SAE form must be completed and returned **within 24 hours of the clinician becoming aware of the event.**

[contact] for the attention of [name]

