3.5 Sample Collection

A 20m1 PaxGene sample is to be collected on one occasion from all patients who have given their informed consent to provide blood samples. PaxGene, samples will be collected during any scheduled study visit as these samples are not time critical. The analysis of these blood samples has not yet been finalised, but we would like to perform some tests that will give us additional information on the effects of surgery and the effects of treatment following surgery on the lymphatic system. We are also interested in finding out through DNA and RNA analysis whether there are any genes that may cause lymphoedema after surgery, or increase the chance of side effects from radiotherapy.

Breast tumour specimens will be collected and, where patients have given their informed consent, these tissue samples may be used for future research.

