10 DEFINITION OF CELLULITIS

Cellulitis of the arm after axillary node clearance is a recognised complication and will be recorded in the study. Hospital admission with cellulitis for intravenous antibiotics should be recorded in the Case Record Form (CRF). Entry criteria have therefore been based on a confirmed diagnosis of cellulitis by a general physician, dermatologist or dermatology nurse, along with a checklist of presenting features that will be used to describe the study population.

To confirm diagnosis of the recent (index) episode of cellulitis lymphangitis,, evidence that the following 4 signs and symptoms were present must be obtained from the patient's notes or through discussion with the patient:

- Presence or history of local warmth and tenderness or acute pain.
- Unilateral erythema, or asymmetrical erythema with the more severe side having a temporal relationship to symptoms.
- New or increased swelling of the arm.
- Constitutional disturbance (e.g malaise, rigors, fever).

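### Section 6.2 defines adverse events by research procedure but 6.3 accepts only device-related ones, so harm from the research blood draw has no stated SAE route to the sponsor, and 6.3 sets two SAE clocks

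*Protocol*

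**What the plan says.** Section 6.2 defines an adverse event broadly, as "any untoward medical occurrence in a participant to whom a research procedure has been administered". Causation is not required, since the definition extends to events of any origin: "including occurrences which are not necessarily caused by or related to that procedure". A few lines later it defines relatedness more narrowly: a related event is one that "resulted from administration of the medical device".

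Section 6.3 restricts reporting to device-related events near its start and again near its end: "NB. Only adverse events e.g. illness, injury and accident specifically related to the device should be reported". Immediate SAE reporting is likewise limited to device-related SAEs. There is also an exemption: "Do not report any complications or side effects commonly associated with cancer and/or chemotherapy e.g. septicaemia, neutropenia, deep vein thrombosis". The SAE form asks for "outcome and causality (i.e. unrelated, unlikely, possible, probably, definitely and not assessable".

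The same section says that the sponsor will give the main REC a yearly report covering every SAE, and that investigators should report whatever SAEs their REC or R&D office requires. On timing, the first option for sending the form allows 24 hours or, alternatively, the following working day. The closing line allows 24 hours from the moment the clinician learns of the event.

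Two other sections bear on this. Section 3.5 provides for one research blood sample from women who consent to it: "PaxGene, samples will be collected during any scheduled study visit". Section 10 makes arm cellulitis a recorded study item: "Hospital admission with cellulitis for intravenous antibiotics should be recorded in the Case Record Form (CRF". Section 3.6 sends a copy of the CRF to the central trials unit.

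**The concern.** A broad definition followed by a narrower reporting rule is acceptable if the narrow rule still covers every procedure the study adds. Here it does not. The blood draw is done for research and involves a needle, yet the filter is worded around a device. A site that follows 6.3 literally would not send the sponsor a serious event caused by the draw.

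The yearly ethics report has the same problem. A report on every SAE cannot be built from a stream limited to events that sites have already judged device-related. The ethics committee could read the report as complete when it is not.

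The two deadlines mean that one site can be late under one sentence and on time under another.

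**Working it through.** The plan gives no figure to reproduce on this point, so the check follows each kind of event through the text.

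**1. Harm from the research blood draw (3.5).**
- Definition in 6.2: met, because blood sampling is a research procedure.
- Filter in 6.3: failed, because the harm is not related to a device. Section 6.3 does not say which device it means, but neither the bioimpedance unit nor the perometer takes blood.
- Other route: the line on SAEs required by the REC or R&D office. It may catch some events but does not name the sponsor.
- Result: no stated SAE route to the sponsor.
- Number exposed: at most 1100 + 300 = 1400 women, one draw each. Sampling needs separate consent (Consent Form B, in the notes to the schedule in section 2.0), and no uptake is given. The true number is therefore unknown and 1400 is only a ceiling.

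**2. The yearly ethics report (6.3).**
- Promised content: every SAE.
- What sites send the sponsor: device-related SAEs only.
- Result: the content is wider than the input, so the report cannot be compiled as described.

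**3. Arm cellulitis with hospital admission (10, 3.6, 6.2, 6.3).**
- Section 10: recorded, with admission for intravenous antibiotics entered in the CRF.
- Section 3.6: a copy of the CRF goes to the trials unit.
- Section 6.2: inpatient admission meets the seriousness criterion.
- Section 6.3: an SAE form is sent only if the site already judges the event device-related.
- Result: the event is captured centrally, but without expedited reporting or a causality assessment unless the site has made that judgement.

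**4. The two clocks (6.3).** Assume, for illustration, that the clinician learns of an event on Friday at 17:00.
- 24 hours from awareness ends on Saturday at 17:00, which is 24 hours.
- The following working day, if it ends on Monday at 17:00, gives 3 × 24 = 72 hours.
- Difference: 72 − 24 = 48 hours. From Monday to Thursday the two nearly coincide. The telephone route, in which the form follows within 24 hours of the call, fits the awareness clock if the call is prompt.

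**The case against.** The best defence is that bioimpedance is non-invasive, treatment decisions rest on the perometer, and no primary or secondary objective concerns safety. A study of this kind may choose a narrow reporting rule, and few events are expected. That argument stands as to scale. It does not explain why the one research procedure with a needle falls outside the rule, or how the yearly report can be wider than what sites send. The yearly report might be read as covering only the SAEs received, in which case the text should say so.

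Several stronger readings are tempting, and the protocol does not support them.
- **A reader might infer that blood-draw harm or septic cellulitis never reaches the sponsor's side.** Cellulitis admissions reach the trials unit through the CRF, and the REC or R&D line may catch some blood-draw SAEs.
- **A reader might infer that septicaemia is both required and forbidden.** It is listed as an example of a complication of cancer or chemotherapy. Sepsis from a device injury can fairly be read as reportable, although the text does not say so.
- **A reader might infer that the data monitoring committee sees only device-labelled events.** Section 13.2 has it review the trial data, with no limit to SAE forms.
- **A reader might infer that half of the causality scale cannot be used.** An event sent on suspicion can later be graded unlikely or not assessable, and an unused grade loses no data.

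It is also fair to say that any relatedness filter leaves a first judgement with the site. The fix below lowers that threshold but does not remove it.

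**Conclusion.** The point holds in a limited form. Sections 6.2 and 6.3 do not match in scope, harm from the research blood draw has no stated SAE route to the sponsor, and the yearly ethics report cannot be compiled as promised. The two SAE deadlines differ by up to about 48 hours in the weekend example. Arm cellulitis with admission is captured, but as a CRF item rather than as an SAE with a causality assessment, unless the site already sees a device link.

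The practical size is small. The procedures are low-risk, and the number of blood draws cannot be derived from the protocol. The conclusion assumes that the device in 6.3 does not include blood-sampling equipment and that CRF data held by the trials unit are available to the sponsor. No efficacy or diagnostic-accuracy result depends on it. It is still worth correcting, because it is a stated rule that misdirects sites rather than a detail left open.

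**What to change.** Amend section 6.3 in four places.

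1. Replace the device-only restriction, wherever it appears, with events possibly, probably, definitely or not assessably related to any research procedure, and name the procedures: bioimpedance including skin preparation, perometry, and blood sampling. Align the definition of relatedness in 6.2 with this.
2. Make the scope of the yearly REC report the same as the scope of what sites send.
3. State that the cancer and chemotherapy exemption does not apply to an event suspected to be related to a research procedure.
4. Reconcile the two SAE deadlines into a single clock with one starting point.

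Cellulitis without a suspected link to a research procedure can stay a CRF item under Section 10. The cost is a wording amendment, a memo to sites and a small number of extra reports, since unrelated cancer and chemotherapy events remain exempt.
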